5.2.3.2 Dose Reduction Guidelines

Rovalpituzumab tesirine dose reduction for specific toxicities should occur as outlined in Table 5-1 and Table 5-2. If toxicities persist despite dose reduction, the dose should be discontinued. Exceptions to the dose modification guidelines may be permitted with written or electronic approval from the Medical Monitor. If a dose is reduced during the previous cycle, the reduced dose will be administered on Day 1 of subsequent cycles.

Table 5-1 Dose Reductions for Rovalpituzumab Tesirine

Starting Dose	First Dose Reduction (reduce dose)	Second Dose Reduction (discontinue dose)
0.3 mg/kg	0.2 mg/kg	Discontinue dosing

Table 5-2 Unacceptable Toxicities Requiring Dose Reduction

Toxicity	Grade ^a / Details
Thrombocytopenia	Grade 4 thrombocytopenia (or Grade 3 thrombocytopenia with bleeding) lasting more than 7 days and/or requiring platelet transfusion
Thrombocytopenia with bleeding	
Neutropenia	Grade 4 neutropenia lasting more than 7 days and/or requiring hematopoietic growth factor rescue, or any febrile neutropenia (Grade 3 or 4 neutropenia with concurrent fever $\geq 38.3^{\circ}\text{C}$)
Febrile neutropenia	
Laboratory abnormality	Grade 2 or higher hypoalbuminemia (in subject with normal baseline albumin levels) Grade 3 or 4 non-albumin laboratory abnormality considered clinically significant and treatment-related
Nonlaboratory toxicity	Grade 3 or 4 nonlaboratory toxicity (including infusion reactions) with the exception of fatigue, asthenia, nausea, or other manageable constitutional symptom
Skin toxicity	Grade 3 or higher cutaneous toxicity or symptom of photosensitivity (refer to Section 5.5.2)
Serosal effusions	Serosal effusions including: Grade 3 or higher pericardial effusion Grade 2 or higher pleural effusion Grade 3 or higher peripheral edema

a) Refer to Appendix 12.5 for definitions of NCI-CTCAE severity grades.

For the purposes of dose reduction, unacceptable toxicity is defined in Table 5-2. If unacceptable toxicity is encountered in Cycle 1, the Cycle 2 dose may be reduced (Table 5-1). If unacceptable toxicity is encountered at the reduced dose level, treatment should be discontinued. If the rovalpituzumab tesirine dose is reduced, the reduced dose level will be used for any subsequent cycles (i.e., retreatment).

Treatment guidelines for hematologic toxicities, and recommended actions regarding rovalpituzumab tesirine dosing, are outlined in Table 5-3.

Table 5-3 Guidelines for Hematologic Toxicities

Toxicity	Recommended Action ^a for Rovalpituzumab Tesirine Doses
Toxicity on Day 1 of Cycle (i.e., predose of Cycle 2)	
Platelets < 75,000/ μ L	
 • Hold • With resolution restart at original dose for next cycle • If no resolution, reduce dosing
ANC < 1,000/ μ L	
 • Hold • Growth factors are recommended to be used per ASCO/NCCN/institutional guidelines • With resolution restart at original dose for next cycle • If no resolution, reduce dosing
Toxicity on Subsequent Days of Cycle	
Platelets < 25,000/ μ L for greater than 7 days, OR Thrombocytopenia with bleeding observed in the previous cycle	
 • Hold • With resolution restart at reduced dose per Table 5-1 for next cycle • If no resolution, discontinue dosing
ANC < 500/ μ L for greater than 7 days, OR Neutropenic fever (ANC < 1,000/ μ L and single temperature > 38.3°C or temperature > 38.0°C for more than 1 hour)	
 • Hold • Growth factors are recommended to be used per ASCO/NCCN/institutional guidelines^b • With resolution restart at reduced dose per Table 5-1 for next cycle • If no resolution, discontinue dosing

Abbreviations: ANC = absolute neutrophil count.

- a) The maximum allowed dose interruption is 6 weeks.
- b) Colony stimulating factors include filgrastim or sargramostim

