3.2.2 Dose Rationale

The chosen dose regimen, two doses of 0.3 mg/kg administered 6 weeks apart, is based on the safety and efficacy observed in a previous phase 1 study (SCRX16-001), where delayed and/or cumulative toxicities were observed with both q3wk and q6wk schedules and appeared to be related to total dose administered. The total dose was therefore capped at a total cumulative dose of 0.6 mg/kg and the finite dosing regimens of 0.2 mg/kg q3wk for a total of 3 doses (q3wk x 3) and 0.3 mg/kg q6wk for a total of 2 doses (q6wk x 2) were evaluated in expansion cohorts.

Because the intended mechanism of action of rovalpituzumab tesirine is to target cancer stem

cells and, more broadly, tumor-initiating cells, limiting the number of doses is hypothesized to affect anti-tumor response only minimally.

The 0.2 mg/kg q3wk x 3 and 0.3 mg/kg q6wk x 2 dosing regimens demonstrated comparable objective response and clinical benefit rates. Both regimens were tolerated, but the 0.3 mg/kg regimen demonstrated a trend towards lower rates of treatment-emergent adverse events (TEAE), related TEAEs, Grade 3/4 TEAEs and related Grade 3/4 TEAEs. In addition, although the 0.3 mg/kg regimen appeared to have a higher incidence of Grade 3/4 thrombocytopenia, such an AE was generally clinically manageable.

██████████ serosal effusions, which may be life threatening such as leading to pericardial tamponade. In addition, objectives responses preliminarily have appeared to be more durable in subjects treated with the 0.3 mg/kg regimen. Finally, the 0.3 mg/kg q6wk x 2 regimen is more conveniently administered than 0.2 mg/kg q3w x 3 and coincides with the timing of radiographic evaluation of tumor size. Therefore, 0.3 mg/kg q6wk x 2 is the chosen dose regimen for this study.

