5.2.2 Dose and Administration

Dosing is based on subject actual body weight to the nearest tenth of a kilogram, assessed on Day 1 of each cycle, and administered according to the assigned dose.

Subjects must meet all of the following on each dosing day before receiving study drug:

- Absolute neutrophil count (ANC) \geq 1,000/ μ L
- Platelet count \geq 75,000/ μ L
- Clinically-significant AEs occurring during the previous cycle (both clinical and laboratory) have resolved to Grade 0 or 1 (or to baseline grade if preexisting)

Rovalpituzumab tesirine should be diluted into 100 mL normal saline (0.9% NaCl). The infusate should be administered over 30 minutes [REDACTED]

[REDACTED] See the Pharmacy Instructions for details.

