5.2.3 Dose Modifications

5.2.3.1 Treatment Delays Due to Toxicity or Progression

Subjects who experience toxicity during a cycle must have recovered as outlined previously in Section 5.2.2 before the next cycle may proceed. If an AE is still ongoing at the time of the next scheduled cycle, the cycle must be delayed until recovery. Specific recommendations are given below.

In the event of isolated CNS progression during study treatment, rovalpituzumab tesirine may be withheld while palliative treatment is administered, e.g., a standard course of whole brain radiotherapy in accordance with institutional practice. During this time, the subject should be fully evaluated for other sites of PD. If progression is isolated to the CNS, study drug may be restarted 1 week after the completion of radiotherapy. If more than 6 weeks have elapsed since the previous dose of study drug, the subject should undergo a radiographic tumor assessment. If additional sites of PD are present, the subject will be required to discontinue study drug, but may be eligible for retreatment.

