5.5 Management of Adverse Reactions

5.5.1 Management of Serosal Effusions

Serosal effusions (pleural or pericardial, or ascites) have been observed with rovalpituzumab tesirine, alone or in combination with peripheral edema and/or hypoalbuminemia. These events have the potential to be life-threatening (e.g. pericardial tamponade). Therefore, development of any of these events or worsening from baseline warrants prompt evaluation by the Investigator or

designee. Alternative causes, such as infection, congestive heart failure, or disease progression, should be ruled out.

In the event of a grade 2 or higher AE in this group (effusions, edema, hypoalbuminemia) considered related to rovalpituzumab tesirine:

- Systemic corticosteroids, when initiated promptly, have been reported to be beneficial in some prior cases. Consider a tapering regimen, such as dexamethasone up to 8 mg orally twice a day for 5 days, followed by 4 mg orally twice a day for 5 days, then 2 mg orally twice a day for 5 days. Alternatively, nonsteroidal therapies for serositis may be considered, such as non-steroidal anti-inflammatory drugs (NSAIDs, e.g., ibuprofen 400-600 mg orally three to four times daily) or colchicine (e.g. 0.6 mg orally two to three times daily) given for 1-2 weeks.
- Until clinical experience suggests otherwise, guidance for dose delay and/or reduction, as well as criteria for ongoing dosing, should follow Sections [5.2.2](#) and [5.2.3](#).

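### Table 5-2 lists no dose-reduction trigger for isolated, drug-related Grade 3 hypoalbuminemia that worsens from an already abnormal baseline

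*Protocol*

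**What the plan says.** Protocol Section 5.2.3.2 names Table 5-2 as the definition of unacceptable toxicity for dose reduction. The table's laboratory row holds two criteria: "Grade 2 or higher hypoalbuminemia (in subject with normal baseline albumin levels) Grade 3 or 4 non-albumin laboratory abnormality considered clinically significant and treatment-related". Table 5-1 gives one step down, from 0.3 to 0.2 mg/kg, and then discontinuation. The text adds: "If unacceptable toxicity is encountered in Cycle 1, the Cycle 2 dose may be reduced". A reduced dose carries over to later cycles, including retreatment, and the Medical Monitor may approve exceptions.

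Three other sections bear on a low albumin:

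- Section 5.2.2 (redosing): clinically significant AEs from the previous cycle must "have resolved to Grade 0 or 1 (or to baseline grade if preexisting").
- Section 5.2.3.1 (delay): "If an AE is still ongoing at the time of the next scheduled cycle, the cycle must be delayed until recovery".
- Section 5.5.1 (serosal effusions and related events): this asks for prompt evaluation of new or worsening events and gives treatment advice that begins "In the event of a grade 2 or higher AE in this group (effusions, edema, hypoalbuminemia) considered related to rovalpituzumab tesirine". On dosing it refers back: "guidance for dose delay and/or reduction, as well as criteria for ongoing dosing, should follow Sections" 5.2.2 and 5.2.3.

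**The concern.** The two laboratory criteria do not meet. One admits albumin only when the baseline was normal; the other covers severe abnormalities of everything except albumin. A subject who starts below normal and then has a drug-related fall to Grade 3 sits between them.

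Such subjects can enroll, because inclusion criterion 9 in Section 4.1 sets no albumin minimum. Section 5.5.1 covers related hypoalbuminemia of Grade 2 or higher whatever the baseline, but it sends the reduction question to Section 5.2.3, which has no entry for them.

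At stake is the dose given after recovery. Section 3.2.2 reports that "delayed and/or cumulative toxicities were observed with both q3wk and q6wk schedules and appeared to be related to total dose administered", and total dose is what a reduction limits. A site following the table literally could give the full 0.3 mg/kg again after an event more severe than one that is listed. Sites that use their own judgment could differ.

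**Working it through.** The plan gives no figure to reproduce. The check sets the event against every rule that could reduce the dose, then sizes the dose difference.

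**1. The event against each row of Table 5-2.** The event is isolated, treatment-related Grade 3 hypoalbuminemia with baseline albumin below normal.

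| Row | Met? | Reason |
|---|---|---|
| Thrombocytopenia | No | Different analyte |
| Neutropenia | No | Different analyte |
| Laboratory, albumin line | No | Baseline not normal |
| Laboratory, Grade 3 or 4 line | No | Albumin excluded |
| Nonlaboratory | No | Appendix 12.5 places hypoalbuminemia under laboratory events |
| Skin | No | Not a skin event |
| Effusions and edema | No | Event is isolated |

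No trigger is met. Grade 4, defined by life-threatening consequences, or an accompanying effusion or edema would probably meet another row.

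**2. Other sections.** Table 5-3 covers only platelets and neutrophils. Sections 5.2.2 and 5.2.3.1 decide when dosing resumes, not at what dose. Section 5.5.1 refers back to 5.2.2 and 5.2.3. The protocol itself treats a hold and a reduction as separate decisions: for some hematologic events Table 5-3 allows a restart at the original dose after resolution, while for others it says "With resolution restart at reduced dose per Table 5-1 for next cycle".

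**3. Worked examples.** Grades come from Appendix 12.5: Grade 1 is below the lower limit of normal down to 3 g/dL, Grade 2 is below 3 down to 2, and Grade 3 is below 2. The lower limit of 3.5 g/dL is from SAP Appendix E and is an assumption here, since Section 7.6.4 has albumin measured locally. The subjects are hypothetical.

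| Subject | Baseline (g/dL) | Lowest (g/dL) | Fall (g/dL) | Grade reached | In Table 5-2? | Hold ends at |
|---|---|---|---|---|---|---|
| A | 3.5 (normal) | 2.9 | 3.5 − 2.9 = 0.6 | 2 | Yes | 3.0 (Grade 1) |
| B | 3.4 (Grade 1) | 1.8 | 3.4 − 1.8 = 1.6 | 3 | No | 3.0 (Grade 1) |
| C | 2.8 (Grade 2) | 1.8 | 2.8 − 1.8 = 1.0 | 3 | No | 2.0 (baseline grade) |

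B falls further and to a worse grade than A, yet only A is listed. For C the hold ends after a rise of 2.0 − 1.8 = 0.2 g/dL.

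**4. Dose difference.** Full dose against one reduction after Cycle 1:

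- Cycle 2: 0.3 vs 0.2 mg/kg; 0.1/0.3 = 33% less.
- Initial course: 0.3 + 0.3 = 0.6 vs 0.3 + 0.2 = 0.5 mg/kg; 0.1/0.6 = 17% less.
- Four cycles, only if retreated: 4 × 0.3 = 1.2 vs 0.3 + 3 × 0.2 = 0.9 mg/kg; 0.3/1.2 = 25% less.

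**5. A second effect of the same definition.** Section 5.2.3.2 also uses unacceptable toxicity as the reason to stop treatment at the reduced dose. If this event arises in a subject already at 0.2 mg/kg, that rule is not triggered either.

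**The case against.** The strongest reply is that the wording looks deliberate. Limiting one line to normal baselines and excluding albumin from the next shows that albumin was considered separately. At Grade 2 the limit makes sense, because a subject just above 3 g/dL needs only a small drop to cross the threshold. That reason does not extend to a drug-related fall below 2 g/dL, and the documents give no other.

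Other points narrow the concern:

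- **Eligibility.** Inclusion criterion 8 (recovery of clinically significant toxicity to Grade 1) and exclusion criterion 1 (undue risk, including from screening laboratory findings) could keep out some subjects like C. Criterion 8 does not exclude a Grade 1 baseline such as B's, and a Grade 2 baseline due to the disease itself, and not judged an undue risk, can also enter.
- **Frequency.** Section 5.5.1 describes hypoalbuminemia as accompanying effusions, and qualifying effusions or edema already trigger a reduction. The isolated case may be uncommon.
- **Discretion.** Even for listed events, reduction in Cycle 2 is permissive. For unlisted ones, the hold, prompt evaluation, supportive treatment, investigator discontinuation (Section 4.3.1), Medical Monitor exceptions and periodic iDMC safety review all remain.
- **Retreatment.** It requires, among other things, that the subject tolerated the first two doses, so the four-cycle figure may seldom apply.
- **Evidence.** Section 3.2.2 does not name hypoalbuminemia, and nothing in the documents shows that 0.2 mg/kg lowers its recurrence.

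These points limit the weight of the concern. None supplies a reduction trigger for the event.

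**Conclusion.** The gap is real on the text as written: the event meets no criterion in Table 5-2, and no other section fills it. A less severe albumin fall from a normal baseline is listed, so the table ranks the two events the wrong way round.

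The firm stake is the Cycle 2 dose, a difference of 0.1 mg/kg. The difference between listed and unlisted events is in what the table calls for, not in an automatic outcome. The finding of a gap does not depend on the assumed 3.5 g/dL limit; only the example values do. Nor does it depend on Subject C.

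This is a worthwhile, inexpensive safety correction that should be made. It does not affect the trial's endpoints, estimation or error rates.

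**What to change.** Keep the Grade 2 trigger for subjects with a normal baseline. Add one line to the laboratory row of Table 5-2: Grade 3 or 4 hypoalbuminemia, worsened from an abnormal baseline, judged clinically significant and treatment-related. Equivalently, let the existing Grade 3 or 4 laboratory criterion apply to albumin when the baseline was abnormal. Either change also reaches the rule for stopping at the reduced dose, because both rules use the same definition. The medical monitor should confirm the threshold.

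The cost is one line, by amendment or protocol clarification letter. Albumin is already in the chemistry panel (Section 7.6.4), so no new test is needed. The downside is possibly a few more dose reductions.

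### After a brief Grade 4 cytopenia that needed rescue, Protocol Tables 5-2 and 5-3 point to different Cycle 2 doses (0.2 or 0.3 mg/kg), and nothing says which governs

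*Protocol*

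**What the plan says.** Section 5.2.3.2 opens by directing that reductions follow Tables 5-1 and 5-2. Table 5-1 allows one step, from 0.3 to 0.2 mg/kg, and then discontinuation. Table 5-2 is titled "Unacceptable Toxicities Requiring Dose Reduction". Its platelet entry is "Grade 4 thrombocytopenia (or Grade 3 thrombocytopenia with bleeding) lasting more than 7 days and/or requiring platelet transfusion", and its neutrophil entry includes "Grade 4 neutropenia lasting more than 7 days and/or requiring hematopoietic growth factor rescue". The text below the table adds: "For the purposes of dose reduction, unacceptable toxicity is defined in Table 5-2". It then says that if such a toxicity occurs in Cycle 1, "the Cycle 2 dose may be reduced".

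Table 5-3 gives recommended actions for hematologic toxicities in two blocks.

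- **Day 1 block:** platelets below 75,000/µL or ANC below 1,000/µL before the Cycle 2 dose. The advice is to hold the dose, and then: "With resolution restart at original dose for next cycle". If the count does not resolve, the dose is to be reduced.
- **Subsequent Days block:** platelets below 25,000/µL or ANC below 500/µL for more than 7 days, thrombocytopenia with bleeding, or neutropenic fever. The advice is to hold, then restart at the reduced dose once resolved.

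Transfusion and growth-factor rescue do not appear as reduction triggers in Table 5-3. Section 5.2.2 sets the dosing-day criteria ("Subjects must meet all of the following on each dosing day before receiving study drug"), with the same platelet and ANC thresholds as the Day 1 block. Section 5.2.3.1 states: "If an AE is still ongoing at the time of the next scheduled cycle, the cycle must be delayed until recovery".

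**The concern.** In Table 5-2, rescue alone is enough to call for a reduction, because the entries join duration and rescue with and/or. In Table 5-3, rescue plays no part in the choice of dose. A subject with a short Grade 4 event that needed rescue, and with a count still low on Cycle 2 Day 1, therefore meets a Table 5-2 trigger. In Table 5-3 the same subject meets only the row that returns to the starting dose. Two sites could each follow a table in the protocol and give different doses after the same severe cytopenia.

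This concerns a known toxicity. Section 3.2.2 reports that delayed or cumulative toxicity in the phase 1 study looked related to total dose. It also says that the 0.3 mg/kg regimen seemed to produce more Grade 3/4 thrombocytopenia, though this was generally manageable. A reduction also carries into any retreatment. Because Table 5-1 allows only one step, the choice decides whether a later unacceptable toxicity leads to reduction or to discontinuation.

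**Working it through.** No sample-size or error-rate figure is involved. The check sets the two tables side by side and then sizes the dose difference.

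**Can the case occur?** Appendix 12.5 puts Grade 4 at platelets below 25,000/µL and neutrophils below 500/µL. The dosing thresholds in Section 5.2.2 are higher, at 75,000/µL and 1,000/µL. A count can therefore leave Grade 4 within 7 days and still be too low to dose on Cycle 2 Day 1.

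**What each table gives.** All rows assume no bleeding and no fever. Rescue means platelet transfusion for thrombocytopenia and growth factor for neutropenia. Only the cytopenia entries of Table 5-2 are used.

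| Cycle 1 event and Day 1 status | Table 5-2 | Table 5-3 |
|---|---|---|
| Grade 4, 7 days or less, no rescue; low on Day 1, then resolves | no trigger | Day 1 row: 0.3 mg/kg |
| Grade 4, 7 days or less, rescued; recovered by Day 1 | 0.2 mg/kg | no row applies |
| Grade 4, 7 days or less, rescued; low on Day 1, then resolves | 0.2 mg/kg | Day 1 row only: 0.3 mg/kg |
| Grade 4, more than 7 days; low on Day 1, then resolves | 0.2 mg/kg | Day 1 row: 0.3 mg/kg; Subsequent Days row: 0.2 mg/kg |

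The third line is the inconsistency between the tables. Set against the second, it gives an odd ordering: a site following Table 5-3 where it speaks would give the higher dose to the subject who recovers more slowly. The fourth line shows the same gap inside Table 5-3, where two rows apply at once and name different doses.

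**Does the resolution condition remove the problem?** No. Sections 5.2.2 and 5.2.3.1 require recovery before dosing, so a subject dosed under those rules is on the resolved branch. That is the branch that returns to the starting dose.

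**Dose at stake**, from Table 5-1:

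- Cycle 2 dose: (0.3 − 0.2) / 0.3 = 33.3% lower.
- Planned two-dose total: 0.3 + 0.3 = 0.6 mg/kg against 0.3 + 0.2 = 0.5 mg/kg; 0.1 / 0.6 = 16.7% lower.

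**Frequency.** The documents give no rate for these events, so the number of affected subjects cannot be estimated.

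**The case against.** The strongest defence is that the tables differ in force. Section 5.2.3.2 makes Table 5-2 the definition of unacceptable toxicity and says reduction should follow it, whereas Table 5-3 gives only recommended actions. On that reading, Table 5-2 decides whether to reduce, and Table 5-3 advises on holding and restarting. The same section also uses permissive wording for the Cycle 2 reduction ("the Cycle 2 dose may be reduced"), so 0.3 mg/kg need not breach any rule. Part of this stands: a reader might infer two absolute orders in head-on conflict, and the text does not support that. But the softer wording does not reconcile the tables. Table 5-3 positively names the starting dose after an event that Table 5-2 lists as requiring the lower one, and the permissive verb sits beside a directive sentence and a table title that says otherwise.

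A second defence is that a trigger in the preceding cycle naturally outranks a low count on Day 1, since the rows describe different events. That is a sensible rule, but it is not written. It is equally unwritten for subjects who meet both blocks of Table 5-3.

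The remaining defences are that the case is narrow, that both doses are protocol levels, that recovery criteria apply throughout, and that the Medical Monitor may approve exceptions. All are true, and they limit the importance of the point. The exception route does not resolve it, because a site following Table 5-3 would have no reason to think it needed an exception.

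**Conclusion.** The point holds as a narrow inconsistency in dosing guidance. For a rescued Grade 4 cytopenia of 7 days or less, without bleeding or fever, with the count still low on Cycle 2 Day 1 and later resolved, the protocol points to both 0.2 and 0.3 mg/kg and does not say which governs. The same missing precedence affects subjects who meet both the Day 1 and the Subsequent Days rows of Table 5-3. The difference is 33% of the Cycle 2 dose and 17% of the planned initial course.

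This rests on reading and/or in Table 5-2 as making rescue sufficient by itself, on the Appendix 12.5 grade limits, and on leaving the general laboratory row of Table 5-2 aside.

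Four further inferences are not supported.

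- **An effect on efficacy conclusions.** Nothing shows that response rate, survival or the Stage 1 decision would change. The full analysis set (Protocol 9.2.1.6) takes anyone who received any study drug, so the choice of Cycle 2 dose moves no one in or out.
- **Exactly one platelet and one neutrophil scenario.** That count requires assuming that the Subsequent Days row overrides the Day 1 row, which is not stated.
- **Bleeding as a separate error.** Some thrombocytopenia with bleeding triggers only Table 5-3, but Table 5-2 does not forbid reduction there, so the triggers simply add.
- **A wider clash through the general laboratory row.** This depends on reading that row to include platelets and neutrophils, which have their own entries.

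**What to change.** Three wording changes in Section 5.2.3.2:

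1. In Table 5-3, state that the Day 1 rows returning to the starting dose apply only if no Table 5-2 trigger and no Table 5-3 Subsequent Days trigger occurred in the preceding cycle.
2. State that platelet and neutrophil counts are governed by their own Table 5-2 entries and not by its general laboratory row. Without this, the first change could undo the Day 1 ANC row: ANC below 1,000/µL is always Grade 3 or 4 under Appendix 12.5, so any such case judged clinically significant and treatment-related could count as a trigger.
3. Replace the permissive verb for the Cycle 2 reduction with the directive one used at the start of the section, keeping the existing Medical Monitor exception.

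An optional tidy-up is to use one febrile neutropenia definition. Table 5-2 sets fever at 38.3°C or above. Table 5-3 uses a single reading above 38.3°C, or above 38.0°C for more than 1 hour.

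The cost is protocol wording only, with no change to design, sample size or analysis. The downside is less investigator discretion, and a few more subjects may receive 0.2 mg/kg. The documents do not allow that number to be estimated.

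### The Day 1 rows of Protocol Table 5-3 appear to allow a reduced dose for unresolved cytopenia, while Sections 5.2.2 and 5.2.3.1 bar dosing until counts recover

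*Protocol*

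**What the plan says.** Protocol Section 5.2.2 sets a condition for every dose: "Subjects must meet all of the following on each dosing day before receiving study drug". The list that follows includes an ANC of at least 1,000/µL and a platelet count of at least 75,000/µL.

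Section 5.2.3.1 carries this over to the next cycle. A subject with toxicity "must have recovered as outlined previously in Section 5.2.2 before the next cycle may proceed", and "If an AE is still ongoing at the time of the next scheduled cycle, the cycle must be delayed until recovery". It then points the reader to more specific recommendations further on.

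Table 5-3, in Section 5.2.3.2, has two rows for low counts found on Day 1, which the table explains as before the Cycle 2 dose: platelets below 75,000/µL and ANC below 1,000/µL. Both rows begin with a hold. Both then give two outcomes: if the count resolves, resume at the unreduced dose; otherwise, "If no resolution, reduce dosing". The ANC row also recommends growth factors. Footnote a limits any interruption to 6 weeks. The rows for toxicity on later days of a cycle differ: there, failure to resolve leads to discontinuation.

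Section 5.2.3.2 also allows exceptions to the dose modification guidelines with the Medical Monitor's approval.

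**The concern.** A table that separates a resolved branch from an unresolved one, and attaches a dose level to the unresolved one, appears to permit a dose in a subject who is still cytopenic. Sections 5.2.2 and 5.2.3.1 do not permit that at any dose level. A site working from the table and a site working from the sections could therefore handle the same subject differently.

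What is at stake is safety and uniform conduct at an important decision. The initial course has only two doses, so Cycle 2 Day 1 is its one occasion for a between-cycle dose decision. Section 1.1.3 names thrombocytopenia among the drug's remarkable toxicities, and Section 3.2.2 says the chosen regimen appeared to have more Grade 3/4 thrombocytopenia than the alternative schedule. Under Section 5.2.3.2, a reduction also carries forward into any later cycle.

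**Working it through.** No figure in the plan needs to be reproduced. The check compares thresholds and then follows a subject through each provision.

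**Thresholds**

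| Count | Minimum to dose (Section 5.2.2) | Day 1 trigger (Table 5-3) |
|---|---|---|
| Platelets | at least 75,000/µL | below 75,000/µL |
| ANC | at least 1,000/µL | below 1,000/µL |

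Each trigger is the exact complement of the corresponding minimum. A subject who enters a Day 1 row has therefore failed Section 5.2.2, and continues to fail it for as long as the count stays below the row's threshold.

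**Possible courses**

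1. *Count at or above the threshold on Day 1.* The row is not triggered and the count condition of Section 5.2.2 is met. There is no conflict.
2. *Count below the threshold, recovering during the hold.* Sections 5.2.2 and 5.2.3.1 require a delay and then allow dosing. The table says hold, then resume. The provisions agree.
3. *Count below the threshold and still below it.* Section 5.2.2 bars the dose, Section 5.2.3.1 continues the delay, and the table says to reduce dosing. If that means giving a reduced dose now, it cannot be followed together with the two sections.
4. *Count still below the threshold when the 6-week limit is reached.* Section 5.2.2 bars a dose, Section 5.2.3.1 calls for continued delay, footnote a rules out a longer interruption, and the row says reduce. The Day 1 rows do not say which of these governs.

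**Does another reading remove the conflict?** The unresolved bullet might mean that a reduced dose is given once a slow recovery has occurred. Take a subject who recovers partway through the hold. The preceding bullet (resolved, so resume unreduced) describes that subject. The late-recovery reading of the last bullet (slow to resolve, so reduce) would describe the same subject. The two can be separated only by a time at which non-resolution is declared, and the table gives none. Footnote a sets only an outer limit on the hold. This reading would avoid dosing below the threshold, but would leave the dose level undetermined.

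**Scope.** The table's heading for these rows names the dose before Cycle 2. Sections 6.1 and 6.3 put retreated subjects on the same schedule, so the rows extend naturally to the second retreatment cycle. The first retreatment dose is different: Section 4 requires all eligibility criteria to be met again, and Section 4.1 criterion 9 sets platelets of at least 75,000/µL and ANC of at least 1,500/µL.

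**The case against.** The strongest reply is that dosing without recovery is inferred, not stated. Both rows start with a hold. The resolved branch speaks of restarting, while the unresolved branch mentions only a reduction and never tells anyone to give drug below the threshold. Because resolution is undefined, the bullet may simply set the level for a later, permissible dose. This has force: it makes the wording ambiguous and rules out calling the contradiction certain. It does not reconcile the text, because the table does not state that reading and it overlaps with the bullet before it. The later-day rows also treat failure to resolve as an end state.

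A second reply concerns rank. Sections 5.2.2 and 5.2.3.1 use mandatory language, whereas Table 5-3 is titled as guidelines and its column gives recommended actions. A careful site would probably notice this. However, no clause says which prevails, and Section 5.2.3.1 itself directs readers to the specific recommendations.

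Third, the Medical Monitor can approve exceptions. That offers a route for difficult cases, but the Day 1 rows do not depend on such approval, and the clause does not say that it waives the conditions in Section 5.2.2.

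A reader might also infer that every retreatment Day 1 is affected, or that the exposure data would become unreliable. The documents support neither. The first retreatment dose is gated by the eligibility criteria. SAP Sections 6 and 7.4 define cumulative dose from doses actually given and count reductions, interruptions and delays, so differing site practice would be recorded as it happened.

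**Conclusion.** The point holds as a narrow internal inconsistency. Read at face value, the unresolved branch of the two Day 1 rows conflicts with Sections 5.2.2 and 5.2.3.1; on the more generous reading, it leaves the dose unclear. The conclusion assumes that no resolution means the count is still below the row's own threshold. That is the natural reading but not a stated definition, so confidence is moderate rather than high.

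The conflict concerns one dosing occasion in the planned initial course and, by extension, later doses within a course. How many subjects would be affected cannot be derived from the documents. The issue matters for patient safety and for consistent handling across sites. It would be tempting to conclude that the primary results are at risk, but nothing in the documents shows an effect on objective response rate or overall survival. The inconsistency should be corrected, but it does not undermine the trial's analysis.

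**What to change.** Reconcile the unresolved bullet in the platelet and ANC Day 1 rows of Table 5-3 with Sections 5.2.2 and 5.2.3.1 and with the 6-week limit in footnote a, so that a single rule applies. The revised text should define resolution, say when its absence is judged, state what follows if the interruption limit is reached without recovery, and say whether the rows apply to later cycles within a course, including the second retreatment cycle. If any overlap remains between the table and the sections, it should say which prevails. The clinical rule itself is for the sponsor's clinical team to decide.

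The cost is protocol wording, with notice to sites. No analysis, sample size or data collection needs to change.
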